## 17.0 Statistical Considerations

### 17.1 Data Analysis Plan:

The first formal statistical interim analysis is planned on the primary endpoint. This interim analysis is planned to take place when the study is at least 4 months into the study period.

Formal interim analyses of the data will be reviewed by the Data Monitoring Committee. The Committee will be asked to give advice on whether the accumulated data from the study, together with results from other relevant studies, justifies continuing exposure to the study interventions. A decision to modify or discontinue all or some portions of the study will be made only if the result is likely to convince a broad range of experts. In mid-January, 2020, the Data Monitoring Committee will meet to review the interim outcomes analysis.

The final analysis for the primary outcome is planned to take place 12-months after study. The first main report/publication of the study will be prepared when PCPs have completed the 12-month follow-up survey and data for the primary endpoint has been received and cleaned. Longer-term endpoints will be analyzed when all data has been received and cleaned.

An independent Data Monitoring Committee (DMC) will ensure the integrity throughout the study by reviewing outcome data for the study interventions. The DMC will be comprised of a statistician, an expert in behavioral economics interventions in a clinical setting, and a physician with expertise in trials around opioid prescribing interventions. The DMC will review interim and final analysis, data quality and completeness, external factors such as scientific advances which may impact the study and make recommendations. Stopping rules for efficacy or futility will be specified in the charter at the beginning of the study.

#### *Interim Outcome Analysis Plan*

The DMC is responsible for assessment of the efficacy of the interventions during the course of the study i.e. interim analyses of efficacy endpoints. The study protocol version 1.2 pre-specifies the following interim analyses: The DMC will be asked to recommend graduation to the second stage of randomization when there is clear and substantial evidence of a treatment difference. As a guideline, the Lan-DeMets spending function analog of the Pocock boundaries will be used to monitor the primary endpoint comparison for the primary aims. The statistical analysis plan is given in the protocol. In brief, we will fit mixed effects logistic regression models of the primary outcome (described below) for opioid-naïve patients using data from the 12 months of the pre-intervention period, and through December 31, 2020 (approximately 4 months of post-intervention data). These models will include fixed effects for whether or not the encounter was at a clinic in the intervention a given intervention arm or received both interventions, indicators for study month to account for secular trends, and an indicator for whether an observation takes place in an intervention arm clinic and in the post-intervention period. These models will include random effects for clinic and PCP (nested in clinic) to account for within-clinic and within-PCP correlation.

We propose a single interim analysis occurring sometime shortly after January 1, 2021, using data through December 31, 2020. The planned boundaries are given below. The advantage of using the Lan-DeMets spending function is that this permits the DMC during the course of the study to require more frequent interim analysis and preserve type I error. If more interim analyses are desired by the DMC, the Lan-DeMets spending function will be recalculated and provided with each DMC report.

Interim Analysis	Critical Z-score	Nominal One-sided p-vale	Alpha Spent
1	2.16	0.0155	0.0155
Final	2.20	0.0139	0.0095

The analysis of the effect of the intervention on key secondary outcomes will also be provided. Should the stopping boundary be crossed at the proposed interim analysis and there is clear evidence of an intervention's effect, we would recommend the DMC to move into phase 2 of the study in which clinics in the experimental arms for that intervention would be re-randomized to continue with intervention for all opioid prescription or for only 50% of opioid prescriptions. The decision to move to phase 2 will be made separate for each intervention component (choice architecture nudge and PDMP integration/reminders).

We emphasize that data will only be available for the primary outcome in a timely manner for the opioid naïve subpopulation and, therefore, decisions on whether or not to move into stage two of randomization will be made based on that subpopulation only.

The primary outcome for the opioid-naïve subpopulation is: Whether or not an opioid is prescribed in a primary care encounter, *without* currently receiving a non-opioid alternative pain treatment (including a new order for a non-opioid pain treatment).

Key secondary outcomes to be presented to the DMC are:

- The frequency with which each PCP checks the Minnesota Prescription Drug Monitoring Program (derived from the Minnesota PDMP).
- For the opioid-naïve subpopulation, whether a CDC-recommended non-opioid treatment is ordered in a primary care visit (e.g., referral to physical therapy, prescription of an NSAID, referral to pain clinic)
- For the opioid-naïve subpopulation, the length of opioid prescriptions
- For the opioid-naïve subpopulation, the MME of opioid prescriptions

Additionally, there is a possibility that data on two secondary outcomes for the current opioid-using subpopulation will be presented to the DMC:

- Whether there was a partial reduction in the MME or prescription length of refill orders, versus a total opioid discontinuation

- Whether there was an increase in the MME/day for current opioid users with at least 50 MME/day

If at the single interim efficacy analysis, the PDMP integration/reminder intervention show substantial efficacy, we would recommend that the PDMP integration be made available to all clinics. A decision on what constitutes substantial efficacy will be made in consultation with the DMC.

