#### *Primary Outcome Analysis*

To test our primary hypotheses, we will fit mixed effects logistic regression models using data from the 12-month pre-intervention period, and the post-intervention period prior to any second-stage randomization (the model for the current “high risk” opioid group will be multinomial logistic regression due to the 3-category outcome). All models will include fixed effects for whether the encounter was at an intervention arm clinic, an indicator for whether the measurement was after the interventions began, and their interaction. The interaction is the primary measure of the intervention effect. These models include random effects for clinic and PCP (nested in clinic) to account for within-clinic and within-provider correlation. Because of the cluster-randomized design with a moderate number of clinics, residual imbalances in patient and PCP-characteristics among the randomized groups may exist. The primary analysis model will adjust for characteristics at all levels of the hierarchy including clinic-level (indicators for the four systems), PCP-level (clinician type [MD/DO, NP, or PA], sex, and length of tenure in medicine), and patient-level (age, sex, race/ethnicity, insurance status, and in-person or virtual visit). Separate models will be fit to assess the PDMP integration and choice architecture intervention and for the opioid-naïve and current, high-risk opioid users. In each model, the intervention group pools across two arms of the factorial design (e.g., the choice architecture intervention pools across arms 2 and 4) and the control condition pools across the remaining two groups (e.g., arms 1 and 3 to continue the example). A Bonferroni correction will adjust inference for multiple comparison across two different populations (opioid naïve and current, high-risk opioid users) but we will not adjust for multiple tests across the two different interventions.

As an exploratory analysis, we will assess whether PCP characteristics (clinician type and tenure in medicine) and patient characteristics (age, sex, and race/ethnicity) moderate the interventions’ effect. Tests for treatment effect heterogeneity will be implemented by adding the interaction between the potential moderator and the intervention indicator to the models for the primary

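### The final boundary printed in 17.1 for the opioid-naive test (z 2.20) carries no split between populations, 17.3 requires one, and nothing in the documents reconciles the two

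*Combined protocol and SAP*

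**What the plan says.** Section 17.1 (Interim Outcome Analysis Plan) offers, as a guideline, that "the Lan-DeMets spending function analog of the Pocock boundaries will be used to monitor the primary endpoint comparison for the primary aims". The model it describes is for opioid-naive patients. Its table has two rows: interim z 2.16 (nominal one-sided p 0.0155, alpha spent 0.0155) and final z 2.20 (nominal one-sided p 0.0139, alpha spent 0.0095). Only opioid-naive data would be ready in time, so "decisions on whether or not to move into stage two of randomization will be made based on that subpopulation only".

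The stated consequences of a crossing are operational. "The DMC will be asked to recommend graduation to the second stage of randomization", and PDMP integration could be offered to all clinics if it showed substantial efficacy, for which "A decision on what constitutes substantial efficacy will be made in consultation with the DMC". The language around the table is nevertheless that of inference: "Should the stopping boundary be crossed at the proposed interim analysis", and the spending function is preferred because "this permits the DMC during the course of the study to require more frequent interim analysis and preserve type I error".

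Section 17.3 (Primary Outcome Analysis) defines the primary test: "To test our primary hypotheses, we will fit mixed effects logistic regression models", run separately for the two populations and the two interventions. It adds that "A Bonferroni correction will adjust inference for multiple comparison across two different populations", with no adjustment across interventions. It gives no alpha or critical value and does not refer to the 17.1 table. Section 17.1 does not mention Bonferroni. Two-sided 0.05 appears in 17.2, for the power calculations only.

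Section 5.5 records what followed the interim: PMP integration opened to all clinics at month 6, and the second randomization dropped.

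**The concern.** The same final test on the opioid-naive primary outcome has a printed threshold in one section and a multiplicity rule in another that the printed threshold does not satisfy. An opioid-naive result with one-sided p between 0.0125 and 0.0139 could be called significant by the table in 17.1 and, on the most natural reading, not significant under 17.3. The numerical gap is small. But this is the decision rule of a primary test, and if the plan does not settle it, it will be settled with the results in hand. Whether the interim look spends any alpha is also unstated, and that matters more for the error rate than the gap between 2.20 and 2.24.

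**Working it through.** **Inputs.** From 17.1: Pocock-type spending, one interim, z 2.16 and 2.20, alpha spent 0.0155 and 0.0095. From 17.3: Bonferroni over two populations, none over interventions, so error is counted per intervention. From 17.2: two-sided 0.05, for power. Not given: the information fraction t, the correlation between the two populations' test statistics, and the overall alpha for inference.

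**1. Reproduce the printed table.** Spending is α·ln(1+(e−1)t). With α = 0.025 one-sided and t = 0.5 it is 0.025 × ln(1.859) = 0.0155, so z₁ = 2.157. The final value c solves P(Z₁ ≤ 2.157, Z₂ > c) = 0.025 − 0.0155 = 0.0095 with correlation √0.5, giving c = 2.201 (one-sided p 0.0139). This is the printed table. Fractions of 1/3 (2.28, 2.14) and 2/3 (2.07, 2.25) do not fit.

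**2. Is the table already split between populations?** The same function on half the alpha (one-sided 0.0125, t = 0.5) spends 0.00775 at the interim and gives 2.42 and 2.48. The printed values could be a Bonferroni share only if the overall level were two-sided 0.10, which no section states.

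**3. What 17.3 implies on its own.** Two-sided 0.05/2 = 0.025 per population: z = 2.2414, one-sided 0.0125. This needs two assumptions: overall alpha of two-sided 0.05, and no alpha spent at the interim.

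**4. Family error per intervention, interim operational only, current users at 2.2414.** At 2.20 the two-sided level is 2 × 0.0139 = 0.0278.

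| Opioid-naive final z | Independent tests | Upper bound |
|---|---|---|
| 2.2414 | 1 − 0.975² = 4.94% | 0.025 + 0.025 = 5.00% |
| 2.20 | 1 − (1 − 0.0278)(0.975) = 5.21% | 0.0278 + 0.025 = 5.28% |

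Because the correlation is not given, I took a range. At 2.20 the error is 5.17% at correlation 0.2, 5.02% at 0.4 and 4.90% at 0.5; it passes 5% at about 0.42. On the table's one-sided scale the ceiling is 0.0139 + 0.0125 = 2.64% against 2.5%.

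**5. Conditional case: an interim crossing of 2.16 also counts as an efficacy claim.** Bivariate normal with correlation √t, final test two-sided at c, then 1 − (1 − p)(0.975) with the populations independent. For t, I assumed equal monthly visits, variance proportional to 1/12 + 1/m for m post-intervention months, and no allowance for clustering. Four of 12 months gives (1/12+1/12)/(1/12+1/4) = 0.50. Four of 6 months gives (1/12+1/6)/(1/12+1/4) = 0.75, which is relevant to PMP integration because 5.5 opens it to all clinics at month 6.

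| Interim boundary | t | Final 2.2414 | Final 2.20 |
|---|---|---|---|
| Upper only, as printed | 0.50 | 6.0% | 6.3% |
| Upper only, as printed | 0.75 | 5.8% | 6.0% |
| Mirrored (not printed) | 0.50 | 7.1% | 7.4% |
| Mirrored (not printed) | 0.75 | 6.6% | 6.8% |

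The printed interim spend, 0.0155, already exceeds a Bonferroni half of 0.0125. In this case no final value alone restores control; the boundary has to be recomputed for both looks.

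**6. Power cost of 2.24 instead of 2.20.** Φ(1.96 + z_power − c), applied to Exhibit 8 at a 15% reduction. From 96%: 93.5% at 2.20 and 92.9% at 2.24. From 76%: about 68% and 66.5%. Exhibit 8 concerns the prescribing rate rather than the exact primary outcome, so these are indicative.

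**The case against.** The best defence is that the sections do different jobs. Section 17.1 handles repeated looks and is a guideline for the DMC; 17.3 holds the primary analysis and can be read as governing the final test. The second randomization that the boundary was meant to trigger has been dropped, and 17.1 leaves stopping rules to a DMC charter that is not among these documents and may settle the matter. This reading order is reasonable, and the charter cannot be judged here. But 17.1 still prints a row labelled final for this comparison, and neither section says that 17.3 overrides it.

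Three stronger readings are tempting, and the documents do not support them.

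- *Using 2.20 pushes the error above 5%.* Not established. The 5.2% assumes independence and 5.3% is a ceiling. Both populations are seen in the same clinics, and above a correlation of about 0.42 the error is under 5%. What stands is that 2.20 does not give the control under any correlation that a Bonferroni correction is meant to provide.
- *2.24 is the plan's true threshold.* It follows only under the two assumptions in step 3. The two corrections can also be layered, which at t = 0.5 gives 2.48.
- *The real error is 6 to 7%.* That requires an interim crossing to count as an efficacy claim, which no section states. The listed consequences point the other way, although 17.1 also makes the DMC responsible for assessing efficacy and tabulates alpha spent at the interim.

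It is also fair that the effect in the operational case is small, and that leaving the two interventions unadjusted is an open choice which this point does not contest.

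**Conclusion.** The point holds as an unreconciled decision threshold for a primary test. The 2.20 in 17.1 comes from a boundary that gives the full one-sided 0.025 to opioid-naive patients, and 17.3 requires that alpha be shared with current high-risk users. With an operational interim and an overall two-sided 0.05, keeping 2.20 costs at most 0.3 points of family error per intervention and possibly nothing, depending on a correlation that the documents do not give. If the interim carried inference, neither 2.20 nor 2.24 holds 5%: about 5.8 to 6.3% with the printed upper boundary only and 6.6 to 7.4% if mirrored, with the populations independent. Confidence is high that the sections conflict and do not refer to each other. Which value the authors intended cannot be determined from the documents. Severity: minor to should-fix.

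**What to change.** In 17.3:

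1. State the overall alpha per intervention (two-sided 0.05, if that is intended).
2. State whether the interim look spends any of it.
3. Give one final critical value per population. If the interim was operational only, which its stated consequences suggest, this is two-sided 0.025 (z 2.24) for each. Otherwise, use the boundary recomputed on one-sided 0.0125 at the actual information fraction, for both looks; at t = 0.5 that is 2.42 and 2.48.

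In 17.1, remove the final row (2.20) or mark it superseded by 17.3. Cross-refer 17.1, 17.3 and the DMC charter.

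The cost is wording, plus about 0.5 to 1.5 points of power for the opioid-naive test if it moves from 2.20 to 2.24. Current users lose nothing by that move, since under the same assumptions 17.3 already implies 2.24 for them. The interim review has already taken place, so what remains open is the final threshold and the stated status of that look.

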### Futility Analysis

There will be no formal futility analyses presented to the DMC. Given that these interventions have small potential adverse effects, the DMC will NOT be asked to recommend early termination for futility.

17.2 Power Analysis: The proposed design has sufficient power to detect clinically meaningful changes in opioid prescription practices from the main effects of the two interventions and the control group (10). All power calculations assume a two-sided test at the 0.05 significance level. Power for the Primary Aim (comparison of intervention arms to the control during months 1-6) is shown in Exhibits 2a-b assuming a total of 48 clinical are randomized (equal allocation between Arms 1-4) with a conservative estimate of 10 providers per clinic (~12 providers per clinic in the FHS/UMP system). The range of the number of visits eligible and the percentage of visits with an opioid prescription in the control arm (for both the opioid-naïve and opioid-using populations) were based on preliminary data from the EHR from a subset of clinics that will be randomized. Meeker et al. (1) assumed an intra-clinic correlation of 0.05 but that encounters within the same provider were not further correlated. We assumed the correlation for visits within the same clinic (but with different providers) was 0.025 and the within-provider correlation would be 0.075 as well as considering a more conservative scenario (correlation given on the logistic scale (11)). We assumed a 5% and 17% prescription rate in the control arm for the opioid-naïve and opioid-using populations, respectively, based on preliminary analysis of opioid prescribing in Fairview primary care clinics, and based on published research (12). We considered a difference in the percentage of eligible encounters with an opioid prescription between the intervention and control groups of 3.5% and 5% to be of clinical interest in the two populations. Exhibits 8 and 9 demonstrate that we have sufficient power across a wide range plausible scenarios and maintain adequate power even under smaller effect sizes. These calculations are also conservative as they assume 48 clinics, whereas we expect to enroll over 50 clinics.

We also have sufficient power to detect differences between 2.5 to 4 percentage points across the two intervention sets during the first 6 months of the intervention.

Exhibit 8. Power to detect a difference in proportion of eligible visits with an opioid prescription between intervention and control arms. Power calculations assume an opioid prescription rate in the no intervention arms of 7%.									
30 eligible visits/month/provider					15 eligible visits/month/provider				
	% reduction in opioid prescribing					% reduction in opioid prescribing			
Intra-clinic/ Intra-provider correlation	15%	20%	25%	30%	Intra-clinic/ Intra-provider correlation	15%	20%	25%	30%
0.025/0.075	96%	100%	100%	100%	0.025/0.075	76%	95%	100%	100%

Exhibit 9. Power to test a difference in proportion of eligible visits resulting in an opioid prescription between intervention and controls arms in opioid-using population (Primary Aim). Power calculations assume 40 clinics randomized equally to Arms 1-4 with 10 providers/clinic, the opioid prescription rate in the control arm was 17%.									
10 eligible visits/month/provider					5 eligible visits/month/provider				
	Difference in opioid prescription rate between control and intervention					Difference in opioid prescription rate between control and intervention			
Intra-clinic/ Intra-provider correlation	4.5%	5%	5.5%		Intra-clinic/ Intra-provider correlation	4.5%	5%	5.5%	
0.025/0.075	81%	89%	95%	0.025/0.075		77%	86%	93%	

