## 3.0 Study Endpoints/Events/Outcomes

### 3.1 Primary Endpoint/Event/Outcome:

**Opioid-Naïve Population:** Whether or not an opioid is prescribed in a primary care visit, *without* currently receiving a non-opioid alternative pain treatment (including a new order for a non-opioid pain treatment).

**Current Opioid-User Population:** A variable with three mutually-exclusive categories:

Category 1 (appropriate taper): Whether a primary care appointment with someone currently receiving a “high risk” opioid had an order that would reduce MME by no greater than 20%, relative to the current prescription, and there is documented evidence that the reduction was consistent with CDC guidelines. “High risk,” is defined as a patient is currently receiving opioids with >50 MME and/or currently receiving both an opioid and a benzodiazepine.

Category 2 (“inappropriate” taper): Whether a primary care appointment with someone currently receiving a “high risk” opioid had an order that would reduce MME without documented evidence that the reduction was consistent with CDC guidelines, or, decreased MME by greater amounts than recommended (>20% relative reduction in MME).

Category 3 (no taper): Whether a primary care appointment with someone currently receiving a “high risk” opioid had no reduction in MME.

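### The power figures in 17.2 are not for the primary tests in 17.3: wrong significance level, different outcomes, and conflicting base rates and clinic counts

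*Combined protocol and SAP*

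**What the plan says.** **Alpha.** Section 17.2: "All power calculations assume a two-sided test at the 0.05 significance level". Section 17.3, Primary Outcome Analysis: "A Bonferroni correction will adjust inference for multiple comparison across two different populations". It makes no adjustment across the two interventions, so the divisor is two and each test is at 0.025 two-sided. The plan does not print 0.025; it follows from the rule.

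**Outcome.** Exhibit 8 powers the proportion of eligible visits with an opioid prescription. Exhibit 9 powers the proportion "resulting in an opioid prescription between intervention and controls arms in opioid-using population (Primary Aim"). In 3.1 the naïve primary is an opioid prescribed without "currently receiving a non-opioid alternative pain treatment (including a new order for a non-opioid pain treatment"). The user primary is "A variable with three mutually-exclusive categories" (appropriate taper, inappropriate taper, no taper) in patients on a high-risk opioid, and 17.3 analyses it by multinomial regression.

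**Inputs.** Section 17.2: "We assumed a 5% and 17% prescription rate in the control arm" for the naïve and opioid-using populations respectively, whereas Exhibit 8 is captioned 7%. Section 17.2 says the calculations assume 48 clinics and are conservative for that reason; Exhibit 9 is captioned 40.

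**Contrast.** Section 17.3 fits separate models for each intervention, and for naïve patients and "current, high-risk opioid users. In each model, the intervention group pools across two arms of the factorial design". The effect measure is the arm-by-period interaction, with a 12-month pre-period.

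**The concern.** Section 17.2 concludes that power is sufficient over a wide range of scenarios. That conclusion should attach to the tests on which the trial will be judged, and as written it does not. The level is looser than the one to be applied.

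For naïve patients, the powered outcome is broader than the primary one: the primary event rate can be no higher than the any-opioid rate, but how much lower is not stated. For users, whether a prescription was issued is a different outcome from whether and how the dose was tapered. Exhibit 9 also names the opioid-using population, while the test is in high-risk users, and the plan does not say whether its 5 or 10 eligible visits a month are high-risk visits.

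At stake is whether the plan documents what effect the trial was designed to detect on each primary outcome.

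**Working it through.** **Inputs from 17.2 and its exhibits.** Correlation 0.025 within clinic and 0.075 within provider, on the logistic scale; 10 providers per clinic; months 1–6; two-sided 0.05. Exhibit 9: 17% control rate, 40 clinics. Critical values: 1.960 at 0.05, 2.241 at 0.025.

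**Variance components.** Total = (π²/3)/(1 − 0.075) = 3.557. Clinic = 0.025 × 3.557 = 0.0889. Provider = (0.075 − 0.025) × 3.557 = 0.1778.

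**Exhibit 9, reproduced first.** For a post-period comparison, variance per clinic = 0.0889 + 0.1778/10 + 1/[n p(1 − p)], with n = 10 × visits per month × 6. Power = Φ(|difference in logits|/SE − z).

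Example: 17% v 12%, 10 visits, so n = 600. The logit difference is 0.4068. Variance per clinic is 0.1225 (intervention) and 0.1185 (control). With 30 v 10 clinics, SE = √(0.1225/30 + 0.1185/10) = 0.1262 and the ratio is 3.22. Power = Φ(3.22 − 1.96) = 89.7%; Exhibit 9 prints 89%. At 0.025, Φ(3.22 − 2.241) = 83.7%.

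All cells, for differences of 4.5/5/5.5 points:

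| Layout | Alpha | 10 visits | 5 visits |
|---|---|---|---|
| Printed | 0.05 | 81/89/95 | 77/86/93 |
| 30 v 10 | 0.05 | 81.5/89.7/95.0 | 77.5/86.5/92.8 |
| 30 v 10 | 0.025 | 73.1/83.7/91.3 | 68.2/79.4/88.1 |
| 20 v 20 (two arms v two) | 0.05 | 90.8/96.0/98.5 | 87.6/93.9/97.5 |
| 20 v 20 | 0.025 | 85.2/92.8/97.1 | 80.9/89.8/95.3 |
| 36 v 12 (48 clinics) | 0.05 | 87.9/94.2/97.7 | 84.5/91.9/96.3 |

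On its stated inputs, Exhibit 9 fits three arms against one, after the start of intervention. That contrast is inferred from the fit; the exhibit does not state it.

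**Exhibit 8.** Post-period comparisons do not reproduce it. A pre/post interaction does, if clinic and provider effects are stable and so cancel: variance per clinic = 1/[n_pre p0(1 − p0)] + 1/[n_post p(1 − p)].

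Example: 5% base, 24 v 24, 6 + 6 months, 15 visits (n = 900 per clinic and period), 15% reduction. The logit difference is 0.1704, SE 0.0637 and ratio 2.67. Power is Φ(0.71) = 76.2% at 0.05 and Φ(0.43) = 66.7% at 0.025.

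Three layouts fit all eight printed cells (96/100/100/100 and 76/95/100/100) within one point. For the 15% reduction:

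| Layout | 30 visits: 0.05 → 0.025 | 15 visits: 0.05 → 0.025 |
|---|---|---|
| 5%, 24 v 24, 6 + 6 months | 96.6 → 93.8 | 76.2 → 66.7 |
| 7%, 12 v 12, 12 + 6 months (variance at the control rate) | 96.4 → 93.6 | 75.8 → 66.2 |
| 5%, 36 v 12, 12 + 6 months | 96.8 → 94.1 | 76.8 → 67.4 |

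The base rate and contrast behind Exhibit 8 therefore cannot be identified, but the effect of alpha alone is nearly the same in all three.

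**Planned contrast on the powered outcome.** With 24 v 24 clinics, 12 + 6 months and 0.025, the 15%-reduction, 15-visit cell is 79.5% at a 5% base and 92.2% at a 7% base.

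**The 3.5-point naïve difference of interest.** This is a 70% reduction from 5% (3.5/5) or 50% from 7% (3.5/7), beyond Exhibit 8's 15–30% columns. Using the post-period formula with 15 visits and 0.025, power is 99.6% from 7% with 12 v 12 clinics, and 100% to the nearest tenth from 5% or with 24 v 24.

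**The primary outcomes themselves.** No category rates are given for the taper variable and no event rate for an opioid without an alternative, so neither calculation can be made.

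**The case against.** The strongest reply is that nothing here shows too little power. That stands for the powered outcome: with the planned pooling, Exhibit 9 at 0.025 gives values at or above those printed, and the 3.5-point naïve difference is safe. A reader might infer from the fall to 68% that the trial is underpowered. The documents do not support that, because the fall belongs to a three-against-one layout that 17.3 does not use.

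Other points that stand:

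- The 48/40 discrepancy is in the conservative direction: if Exhibit 9 used 40 clinics and more than 50 are expected, it understates power.
- Exhibit 8 names neither population nor clinic count. Reading it as naïve, and so the 5% v 7% conflict, is by elimination. It would also be tempting to say that it used 5% with two arms pooled against two; a fit at the captioned 7% is just as close.
- Exhibit 9 is fitted almost as well by 36 v 12 clinics at 0.025 (81.2/90.1/95.6 and 76.8/86.7/93.4). That contradicts both the stated 0.05 and the captioned 40 clinics, so it would replace one inconsistency with two.
- The interim boundary in 17.1 is described as a guideline. It spends 0.0155 + 0.0095 = 0.025 one-sided with no Bonferroni share, but its final critical value of 2.20 is close to 2.24.
- The last revision (May 2022) came just before data analysis, so restated power cannot alter enrolment, and the confidence interval will show which effects a null result excludes.

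None of this removes the contradictions over alpha, outcome and inputs, and the reassurance on power does not extend to the taper outcome.

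**Conclusion.** The point holds as an inconsistency between sections. The powers in 17.2 are not for the primary tests in 17.3: the level is 0.05 rather than 0.025, the outcomes differ from those in 3.1, and the base rate and clinic count conflict between text and exhibits. The claim that the calculations assume 48 clinics is untrue of Exhibit 9.

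The effect of alpha alone is a loss of about 4 to 9 points in Exhibit 9 and about 9 to 10 points in the lowest cell of Exhibit 8. These sizes rest on a normal approximation, the stated correlations, layouts inferred from fit and, for Exhibit 8, no clinic-by-period variation. The contradictions themselves need no model. Underpowering is not shown. The most serious gap is that the user taper outcome has no power basis at all. The plan should be corrected, but the conduct of the trial is not in question.

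**What to change.** Restate 17.2 in one table for the pooled two-arm v two-arm, pre/post contrast of 17.3 at the Bonferroni-adjusted alpha, with one clinic count and one base rate per population, for the outcomes in 3.1. Take the naïve event rate from pre-period EHR data. For high-risk users, use high-risk visit counts and the EHR rate of MME reduction, and show an assumed range for the share with documented rationale: that share needs chart review (5.2), and no pre-period review is described.

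Correct the sentence that calls the calculations conservative because of 48 clinics, and label Exhibit 8's population and clinic count. As a minor point, state whether the guideline boundary in 17.1 applies within the Bonferroni share.

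The cost is recalculation and rewriting of one section. Some stated powers may become slightly less favourable. Enrolment and conduct do not change.
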